#### 6.3.1.2. Health Assessment Questionnaire Disability Index (HAQ-DI)

The HAQ-DI score is defined as the average of the scores of eight functional categories (dressing and grooming, arising, eating, walking, hygiene, reach, grip, and other activities), administered by the patient. Responses in each functional category are collected as: without any difficulty; with some difficulty; with much difficulty; unable to do a task in that area; and with or without aids or devices. The HAQ-DI score ranges from 0 (no disability) to 3 (completely disabled), when 6 or more categories are non-missing. Detailed algorithm for calculating HAQ-DI score is described in [Appendix 1](#).

The HAQ-DI also includes a separate pain assessment and the patient will be requested to mark the severity of the pain in the past week on a 0-100 VAS, with 0 indicating "no pain" and 100 indicating "severe pain."

[figure not shown]
#### 6.3.2. Analysis Methods for Secondary Efficacy Endpoints

The ACR20 response rates at Week 12 between each of the GS-9876 dosed groups and the placebo group will be compared using a stratified Cochran-Mantel-Haenszel (CMH) chi-square test adjusting for stratification factors in randomization (ie, prior inadequate response to biologic

therapy, yes vs. no; and Geographic region, region 1 vs. region 2 as defined in Section 3.3). The difference in response rates between treatment groups and the corresponding 95% CIs will be presented. The CMH chi-square p-value for testing the superiority of each of the GS-9876 doses as compared to placebo will be provided, as well as the 2-sided 95% exact CI of the ACR20 response rate based on Clopper-Pearson method for each treatment group. Subjects who do not have sufficient measurements to establish efficacy at Week 12 will be considered as failures (ie, non-responder imputation [NRI]). Sensitivity analysis will be conducted by imputing missing components for determining ACR20 as well as early dropouts via the last observation carried forward (LOCF) method.

[figure not shown]
For ACR50 and ACR70 at Week 12, the same CMH approach with NRI as in the analysis of ACR20 described above will be adopted.

The difference in change from baseline in HAQ-DI between each of the GS-9876 dosed groups and the placebo group will be analyzed using a similar MMRM approach as described in Section 6.2.3. The model will include the fixed effects of treatment, visit, treatment by visit interaction, and baseline value. Subjects will be included as a random effect. Missing change scores (eg, due to early withdrawal, etc) will not be otherwise imputed using the MMRM approach.

[figure not shown]
Mean ACR 20/50/70 response rates with NRI will be plotted by treatment and visit. Mean  $\pm$  SD over time will be plotted for each component of ACR 20/50/70.

#### 6.4. Exploratory Efficacy Endpoints

#### 6.4.1. Definition of Exploratory Efficacy Endpoints

PPD

#### 6.4.2. Analysis Methods for Exploratory Efficacy Endpoints

PPD

## 7. SAFETY ANALYSES

### 7.1. Adverse Events and Deaths

#### 7.1.1. Adverse Event Dictionary

Clinical and laboratory adverse events (AEs) will be coded using the MedDRA v 20.0. System organ class (SOC), high-level group term (HLGT), high-level term (HLT), preferred term (PT), and lower-level term (LLT) will be provided in the AE dataset.

#### 7.1.2. Adverse Event Severity

Adverse events are graded by the investigator as Grade 1, 2, 3, 4, or 5 according to toxicity criteria specified in the protocol. The severity grade of events for which the investigator did not record severity will be categorized as “missing” for tabular summaries and data listings. The missing category will be listed last in summary presentation.

#### 7.1.3. Relationship of Adverse Events to Study Drug

Related AEs are those for which the investigator selected “Related” on the AE CRF to the question of “Related to Study Treatment.” Relatedness will always default to the investigator’s choice, not that of the medical monitor. Events for which the investigator did not record relationship to study drug will be considered related to study drug for summary purposes. However, by-subject data listings will show the relationship as missing.

#### 7.1.4. Serious Adverse Events

Serious adverse events (SAEs) will be identified and captured as SAEs if AEs met the definition of an SAE specified in the study protocol. SAEs captured and stored in the clinical database will be reconciled with the SAE database from the Gilead Drug Safety and Public Health (DSPH) Department before data finalization.

#### 7.1.5. Treatment-Emergent Adverse Events

##### 7.1.5.1. Definition of Treatment-Emergent Adverse Events

Treatment-emergent adverse events (TEAEs) are defined as one or both of the following:

- Any AEs with an onset date on or after the study drug start date and no later than 30 days after permanent discontinuation of study drug
- Any AEs leading to premature discontinuation of study drug

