##### 7.1.5.2. Incomplete Dates

If the onset date of the AE is incomplete and the AE stop date is not prior to the first dosing date of study drug, then the month and year (or year alone if month is not recorded) of onset

determine whether an AE is treatment emergent. The event is considered treatment emergent if both of the following 2 criteria are met:

- The AE onset is the same as or after the month and year (or year) of the first dosing date of study drug, and
- The AE onset date is the same as or before the month and year (or year) of the date corresponding to 30 days after the date of the last dose of study drug

An AE with completely missing onset and stop dates, or with the onset date missing and a stop date later than the first dosing date of study drug, will be considered to be treatment emergent. In addition, an AE with the onset date missing and incomplete stop date with the same or later month and year (or year alone if month is not recorded) as the first dosing date of study drug will be considered treatment emergent.

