### **7.1.6. Summaries of Adverse Events and Deaths**

Treatment-emergent AEs will be summarized based on the Safety Analysis Set.

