#### **7.1.6.1. Summaries of AE incidence in Combined Severity Grade Subsets**

The number and percentage of subjects who experienced at least 1 TEAE will be provided and summarized by SOC, HLT, PT, and treatment group. For other AEs described below, summaries will be provided by SOC, PT, and treatment group:

- TEAEs of Grade 3 or higher (by maximum severity)
- TEAEs of Grade 2 or higher
- All Treatment Emergent (TE) treatment-related AEs
- TE Treatment-related AEs of Grade 3 or higher (by maximum severity)
- TE Treatment-related AEs of Grade 2 or higher
- All TE SAEs
- All TE treatment-related SAEs
- All TEAEs leading to premature discontinuation of any study drug
- All TEAEs leading to premature discontinuation of study
- All TEAEs leading to death (ie, outcome of death)
- All TEAEs leading to temporary interruption of any study drug

A brief, high-level summary of AEs described above will be provided by treatment group and by the number and percentage of subjects who experienced the above AEs. All deaths observed in the study will be also included in this summary.

Multiple events will be counted only once per subject in each summary. Adverse events will be summarized and listed first in alphabetic order of SOC and HLT within each SOC (if applicable), and then by PT in descending order of total frequency within each SOC. For summaries by severity grade, the most severe grade will be used for those AEs that occurred more than once in an individual subject during the study.

In addition to the above summary tables, all TEAEs and TE treatment-related AEs will be summarized by PT only, in descending order of total frequency.

In addition, data listings will be provided for the following:

- All AEs, indicating whether the event is treatment emergent
- All AEs of Grade 3 or higher
- All AEs of Grade 2 or higher
- SAEs
- Deaths
- AEs leading to death (ie, outcome of death)
- AEs leading to premature discontinuation of any study drug
- AEs leading to premature discontinuation of study
- AEs leading to temporary interruption of any study drug

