#### **7.2.2.1. Treatment-Emergent Laboratory Abnormalities**

Treatment-emergent laboratory abnormalities are defined as values that increase at least 1 toxicity grade from baseline at any postbaseline time point, up to and including the date of last dose of any study drug plus 30 days for subjects who permanently discontinued study drug, or the last available date in the database snapshot for subjects who were still on treatment at the time of an interim analysis.

If the relevant baseline laboratory value is missing, any abnormality of at least Grade 1 observed within the time frame specified above will be considered treatment emergent.

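### An adverse event with a complete pre-dose onset date is treatment-emergent only if study drug was stopped for it, so one that causes an interruption, or worsens on its original record, is left out of the TEAE tables

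*SAP*

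**What the plan says.** SAP 7.1.5.1 opens with "Treatment-emergent adverse events (TEAEs) are defined as one or both of the following" and gives two criteria. The first is an onset window: "Any AEs with an onset date on or after the study drug start date and no later than 30 days after permanent discontinuation". The second has no onset condition: "Any AEs leading to premature discontinuation of study drug". There is no third.

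Section 7.1.5.2 deals with incomplete dates. Provided the stop date is not before the first dose, an incompletely dated event passes the lower limit if "The AE onset is the same as or after the month and year (or year) of the first dosing date of study drug". The upper limit is handled in the same way.

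Section 7.1.6 says "Treatment-emergent AEs will be summarized based on the Safety Analysis Set". In 7.1.6.1 the tables by grade, seriousness, death, study discontinuation and interruption all cover treatment-emergent events only, for example "All TEAEs leading to temporary interruption of any study drug". The same section also provides listings of all adverse events with a treatment-emergent flag, and of Grade 2 or higher and Grade 3 or higher events, SAEs, deaths and events leading to interruption. It counts every death in the high-level summary.

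For laboratory data, 7.2.2.1 uses a worsening rule: "values that increase at least 1 toxicity grade from baseline at any postbaseline time point".

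**The concern.** The second criterion shows that the plan accepts that an event which began before dosing can matter once the subject is on drug. It recognises this for one consequence only, permanent withdrawal of study drug. The same event with a different consequence, such as an interruption or a rise from Grade 1 to Grade 3, falls outside the definition. Entry to the incidence tables then depends on what was done with study drug rather than on how the event behaved.

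Two neighbouring tables in 7.1.6.1 therefore draw on different event populations. The drug-discontinuation table can include pre-dose events; the interruption table cannot, if their onset dates are complete.

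Safety and tolerability is a secondary objective (SAP 1.1). The by-arm comparison of adverse events is made in the incidence tables, so an omission there is an under-count in the comparison even though the event is listed elsewhere.

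**Working it through.** The plan gives no figure to reproduce, so the check is one of logic.

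**Inputs.** The two criteria in 7.1.5.1, the date rules in 7.1.5.2, the table and listing specifications in 7.1.6.1, and 20 subjects per arm (SAP 1.2 and 1.3).

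**Step 1. Apply both criteria to an event with a complete onset date before the first dose.** The onset criterion fails in every row, so only the discontinuation criterion can admit it.

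| Course on treatment | Led to stopping drug? | TEAE? | Result in 7.1.6.1 |
|---|---|---|---|
| Drug stopped because of the event | Yes | Yes | In every applicable table |
| Drug interrupted, then resumed | No | No | Absent from the interruption table |
| Grade rises, same record, drug continued | No | No | Absent from the Grade 2 or higher and Grade 3 or higher tables |
| Becomes serious, same record, drug continued | No | No | Absent from the SAE table |
| Fatal, stopping of drug not recorded as the action | No | No | Absent from the fatal-TEAE table; death counted in the high-level summary |
| Fatal, or leaves the study, with stopping of drug recorded | Yes | Yes | In every applicable table |

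**Step 2. Change only the completeness of the onset date.** Suppose the event is dated only to the month of the first dose and had not resolved before dosing. Section 7.1.5.2 then classes it as treatment-emergent, even if it really began before the first dose. The gap in Step 1 is therefore confined to complete pre-dose onset dates (and to partial dates in an earlier month or year).

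**Step 3. Change only how worsening is recorded.** If a site enters the worsening as a new event with its own onset date on treatment, the new record meets the onset criterion. Rows 3 and 4 then leave no gap, so far as the worsening or new seriousness prompts a new record. Row 2 may remain, because an interruption without a change of grade gives no obvious reason to open a new record.

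**Step 4. Scale.** One subject in an arm of 20 is 1/20 = 0.05, or 5 percentage points of incidence in each table concerned. This is the unit in which an omission would appear. It does not estimate how many omissions there would be, and the SAP gives nothing from which to estimate that.

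**Step 5. Apply the criterion proposed under the fix.** Rows 2 to 5 become treatment-emergent if the change in the event falls between the first dose and 30 days after the last dose. Rows 1 and 6 are unchanged. Events that begin after the 30-day window are not drawn in, because the criterion applies only to onset before the first dose.

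**The case against.** The strongest reply is that the gap depends on data-collection rules that are not in the SAP. How a site records a worsening event is normally settled in the protocol or eCRF instructions. If those call for a new record, the grade and seriousness parts disappear. That stands, and it limits the size of the point. It does not clearly reach interruptions without a grade change, and the SAP does not state the convention on which its definition would then rely.

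A second reply is that nothing is hidden. This also stands. The listings are not restricted to treatment-emergent events, all deaths are in the high-level summary, and with 20 subjects per arm the listings can be read in full. They do not, however, give incidence by arm.

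A third reply is that deaths and study exits on treatment usually end dosing, and so usually meet the discontinuation criterion. That is fair. A fatal event escapes only if the recorded action is something else, so these cases add little.

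A reader might also infer that the laboratory rule in 7.2.2.1 contradicts the adverse event rule. The SAP does not support that. Laboratory values are repeated measurements with a defined baseline, so a grade shift can be computed directly, whereas adverse events are reported with an onset date. The contrast shows that the plan counts worsening elsewhere; it is not an inconsistency that has to be resolved.

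**Conclusion.** The point holds in a limited form. For a complete onset date before the first dose, 7.1.5.1 admits an adverse event only through discontinuation of study drug. An event that leads to an interruption, or that worsens or becomes serious on its original record, is absent from the TEAE tables. This is a rule as stated, not a missing detail.

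Its size is unknown. It is 5 percentage points per affected subject per arm of 20, and may be zero subjects. The conclusion assumes that some pre-dose events are in the database and, for the worsening part, that they stay on one record.

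Two stronger readings are not supported. One is that every pre-dose event is excluded unless drug was stopped; 7.1.5.2 admits some with incomplete dates. The other is that the rule biases the comparison between arms; the same rule applies to all arms of a randomized, double-blind trial, and nothing in the SAP shows a differential effect. The point does not touch efficacy, power or type I error. It is a minor improvement to safety reporting.

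**What to change.** Add one time-bounded criterion to 7.1.5.1, for example: *any AE with onset before the first dose that, on or after the first dose and no later than 30 days after the last dose of any study drug, increases in severity grade, becomes serious, is fatal, or leads to temporary interruption of any study drug.*

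Add a sentence on recording: where worsening is entered as a new adverse event with its own onset date, say so and count only the new record, so that one worsening is not flagged twice.

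The time limits matter. Simply adding interruption, study exit and death to the existing second criterion, which has no time limit, would also make late post-treatment events treatment-emergent.

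The cost is one definition and one derived flag, built mostly from fields that the 7.1.6.1 tables already need (grade, seriousness, outcome, action with study drug). Reported TEAE counts may rise slightly. The date of worsening or of becoming serious is needed where it is recorded; where it is not, the SAP should state the convention used.

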##### 7.1.5.2. Incomplete Dates

If the onset date of the AE is incomplete and the AE stop date is not prior to the first dosing date of study drug, then the month and year (or year alone if month is not recorded) of onset

determine whether an AE is treatment emergent. The event is considered treatment emergent if both of the following 2 criteria are met:

- The AE onset is the same as or after the month and year (or year) of the first dosing date of study drug, and
- The AE onset date is the same as or before the month and year (or year) of the date corresponding to 30 days after the date of the last dose of study drug

An AE with completely missing onset and stop dates, or with the onset date missing and a stop date later than the first dosing date of study drug, will be considered to be treatment emergent. In addition, an AE with the onset date missing and incomplete stop date with the same or later month and year (or year alone if month is not recorded) as the first dosing date of study drug will be considered treatment emergent.

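### An adverse event with no onset date and a complete stop date on the first dosing day meets no treatment-emergent date rule, although the neighbouring rules include that day

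*SAP*

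**What the plan says.** SAP section 7.1.5.1 defines a treatment-emergent AE in two limbs. The first rests on the onset date: "Any AEs with an onset date on or after the study drug start date", up to 30 days after permanent discontinuation. The second takes in any AE that led to premature discontinuation of study drug, whatever its dates.

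Section 7.1.5.2 then deals with dates that are partial or absent:

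- **Partial onset.** The rule opens with "If the onset date of the AE is incomplete and the AE stop date is not prior to the first dosing date of study drug". The known month and year (or year) of onset must then lie between that of the first dose and that of 30 days after the last dose.
- **Onset missing, complete stop date.** The event counts if it is one "with the onset date missing and a stop date later than the first dosing date of study drug".
- **Onset missing, partial stop date.** The event counts if it has an "incomplete stop date with the same or later month and year" (or year) relative to the first dose.
- **Both dates missing.** "An AE with completely missing onset and stop dates" counts.

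Sections 7.1.6 and 7.1.6.1 base the AE summary tables on treatment-emergent events. The high-level summary also includes all deaths. The listings cover all AEs, with a flag for treatment emergence.

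**The concern.** Four of these rules let an event through at the boundary, and one does not. The exception is the rule for a missing onset with a complete stop date, which asks for a stop strictly after the first dosing day. An event with no onset recorded that stopped on that day may have begun after the first tablet was taken. It nevertheless qualifies under no date rule.

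The result is also out of order. With the onset missing, a stop known only to the month of first dose is enough, and so is no stop date at all. A stop recorded exactly as the first dosing day is not.

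What is at stake is the content of the treatment-emergent tables, including those for serious events and for Grade 3 or higher, in a study where safety and tolerability is a secondary objective (section 1.1). A date derivation of this kind is likely to be programmed as written, so the text should settle the case.

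**Working it through.** The point rests on date logic, and the SAP has no figure to reproduce.

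**Inputs.** The two limbs of section 7.1.5.1 and the four rules of section 7.1.5.2, as set out above. For illustration the first dose is placed on 15 March 2017 and the last on 6 June 2017; these dates are assumptions.

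**Step 1. Apply the rules.** Four onset states were crossed with six stop states, giving 4 × 6 = 24 combinations. TE means treatment-emergent; none of these events is assumed to have led to discontinuation.

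| Onset recorded | Stop 14 March | Stop 15 March (Day 1) | Stop 16 March | Stop March 2017 | Stop 2017 | Stop missing |
|---|---|---|---|---|---|---|
| 15 March 2017 | TE* | TE | TE | TE | TE | TE |
| March 2017 | not TE | TE | TE | TE | TE | TE |
| 2017 | not TE | TE | TE | TE | TE | TE |
| Missing | not TE | **not TE** | TE | TE | TE | TE |

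*An impossible record (stop before onset), kept only to complete the grid.

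**Step 2. Check that nothing else catches the bold cell.** The first limb of section 7.1.5.1 needs an onset date. The partial-onset rule needs at least a year of onset. The partial-stop rule does not apply to a complete date. The both-missing rule needs the stop to be missing too. Only the second limb can bring the event in: with discontinuation of study drug added, the same record becomes TE.

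**Step 3. Change the strict condition to an inclusive one.** If a stop on or after the first dosing date qualifies, the bold cell becomes TE and the other 23 combinations are unchanged. In particular, a missing onset with a stop on 14 March stays not TE.

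**Step 4. Size.** Section 1.2 plans 20 subjects per arm. One subject is 1/20 = 5 percentage points of an incidence row. Section 7.1.6.1 counts a subject once per summary, so the shift is 5 points only if the subject has no other treatment-emergent event in that row; otherwise it is 0. For overall incidence, it takes a subject with no other treatment-emergent event at all.

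**The case against.** The comparison with the neighbouring rules can be challenged. In the partial-onset rule, the condition "the AE stop date is not prior to the first dosing date of study drug" is only an entry test: the known part of the onset must then agree with a start in or after the month or year of first dose. When the onset is wholly missing there is no such evidence. The partial-stop rule is generous because a stop somewhere in March may fall well after a dose on 15 March, whereas an exact stop on 15 March leaves only the dosing day. An event of unknown onset that ended that day may equally be a pre-dose complaint that resolved. A strict boundary could then be a deliberate convention. Moreover, section 7.1.5.2 never says that this case is not treatment-emergent; it simply does not name it.

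Part of this stands. The exclusion is an inference from silence, and the evidence in the neighbouring cases does differ. But the SAP gives no reason for treating Day 1 differently here. The partial-stop rule also does not depend on the stop possibly being later: if the first dose falls on the last day of a month, a stop known only to that month cannot be after Day 1, yet it counts. Elsewhere the SAP resolves missing information towards inclusion. An unrecorded relationship counts as related (section 7.1.3), a graded laboratory abnormality with no baseline counts as treatment-emergent (section 7.2.2.1), and a medication started and stopped on the first dosing day counts as concomitant (section 7.4.2).

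Opportunities to recover a missing onset also exist: queries are resolved or adjudicated before the final analysis (section 2.2), and serious events are reconciled with the safety database (section 7.1.4). These make the case rarer but do not decide how a remaining record is classified.

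**Conclusion.** The point holds as a minor inconsistency in wording. A wholly missing onset with a complete stop date on the first dosing day meets no treatment-emergent date rule, and this departs from the inclusive boundary used around it. The effect is confined to one of the 24 combinations examined. Its maximum size is 5 percentage points in one arm's row per affected subject, assuming 20 subjects in the arm and no other treatment-emergent event for that subject in that row. The SAP gives no count of such records; that they are rare is a judgement.

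A reader might infer that first-dose reactions in general drop out of every AE table. The SAP does not support that. A reaction with a recorded Day 1 onset is treatment-emergent, and so is one with a partial onset in the month or year of first dose and a Day 1 stop. An event that led to discontinuation of study drug stays in through the second limb, all deaths enter the high-level summary, and the listings show every AE. Efficacy analyses are not touched.

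**What to change.** In section 7.1.5.2, in the rule for a missing onset with a complete stop date, replace *later than* the first dosing date by *on or after* the first dosing date. This brings the rule into line with the main definition and the adjacent rules, and it reclassifies only the one combination.

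The cost is a few words in the SAP and the matching line in the derivation. The downside is that some events that began before dosing and resolved on Day 1 would be counted as treatment-emergent. That errs on the conservative side for safety, as the SAP's other missing-data conventions do.
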